3.3.3.3.1 Recommended measures in case of eye dryness and ocular hypertension

Changes in tear production as evaluated by the Schirmer test and in intraocular pressure (IOP) are not expected to occur as a direct consequence of anetumab ravtansine therapy. However, IOP may increase in some patients as a consequence of the therapy with topical steroid eye- drops. Since these drugs may be required to manage the corneal epitheliopathy syndrome, IOP will be monitored during this study for patients receiving topical steroid eye drops.

Changes in IOP should be managed by an ophthalmologist/ optometrist. The remedial therapy should be chosen at investigator's discretion or according to the institutional standards; therapeutic measures can include modification of the type or posology of topical steroid eye drop, initiation of topical IOP lowering drugs and any other therapeutic options according to the standard of care. Ophthalmological monitoring should be maintained until the IOP has returned to normal values.

Reductions in tear production evaluated by the Schirmer test, while not being a part of the corneal epitheliopathy syndrome, are a risk factor for developing ocular surface disease including corneal epithelial defects. Therefore, the tear production will be evaluated in this study to determine if changes in this parameter may be helpful to identify patients at higher risk of developing the corneal epitheliopathy syndrome. Abnormal values in the Schirmer test should be evaluated and managed by an ophthalmologist/ optometrist to provide adequate protection to the corneal epithelium. The remedial therapy for the treatment-emergent changes in the Schirmer test (dry eye) should be chosen at investigator's discretion or according to the institutional standards. These measures may include topical lubricants such as eye drops and ointments, punctual occlusion, use of therapeutic contact lenses and any other treatment approaches according to standard of care.

3.3.4 Continuation of treatment with anetumab ravtansine

Treatment with an etumab ravtansine could be re-started at the appropriate dose if the TEAE requiring dose modification has resolved to Grade ≤ 2 within 6 weeks after the last dose of an etumab ravtansine.

3.3.5 Permanent discontinuation of anetumab ravtansine due to TEAEs

- CTCAE Grade 4 non-hematological AE and Bayer Grade 4 corneal epitheliopathy (see Table 9) (except at the investigator's discretion in case of certain Grade 4 abnormality of laboratory assessments, such as abnormal laboratory assessments without corresponding clinical symptoms, or abnormal laboratory assessments that can be easily clinically managed).
- If any type of TEAE requiring dose modification does not resolve to Grade ≤ 1 (or Hb ≥ 9 g/dL in case of anemia) within 6 weeks after the last dose of anetumab ravtansine.
- Delay in anetumab ravtansine administration of 3 weeks (max. 6 weeks between 2 infusions of study drug).
- TEAE requiring dose reduction when already at the 4.5 mg/kg Q3W dose level (minimum dose).
- More than 2 dose reductions required due to a TEAE.

3.4 STUDY CALENDAR

1 cycle = 3 weeks (21 days)

Screening and baseline evaluations are performed per the timeframes indicated in sections 2.2 and 2.4 respectively.

On therapy assessments may be performed up to 5 days prior to indicated time; safety follow up may occur up to 7 days after indicated time; long term follow up phone calls may be performed within \pm 14 days of indicated time.

Dosing cycles after cycle 1 may be delayed for up to two weeks to accommodate schedule conflicts, Federal holidays and inclement weather, etc.

			Cycle 1	1	Sub	sequent Cyc	cles	Ender	Post Therapy Follow-up	
Procedure	Screening/ Baseline	Day 1	Day 8	Day 15	Day 1	Day 8	Day 15	Treatment	30 day safety follow up	Long term follow up
History and $PE^{\underline{1}}$	Х	Х	Х		X				Х	
Weight		Х			Х				Х	
Vital signs	Х	Х	Х		Х				Х	
ECOG Performance Score	Х									
Confirmation of dx and mesothelin expression	Х									
Imaging assessments ²	Х	Ever	y 6 week Y	ts (first 6 n year 2), eve	nonths), every ery 12 weeks t	9 weeks (un hereafter	til end of			
Echocardiogram	Х	Ever	y 6 weel	ks for the	first 6 months, thereafter	, then every	12 weeks			
12 lead ECG^3	Х	Х			X (cycle 2 only)				Х	
HBsAg, anti-HCV, anti-HIV	Х									
Ophthalmologic exam ⁴	Х				Х				Х	

			Cycle	1	Subsequent Cycles Fol		Post T Follo	herapy w-up		
Procedure	Screening/ Baseline	Day 1	Day 8	Day 15	Day 1	Day 8	Day 15	Treatment	30 day safety follow up	Long term follow up
CBC with differential, Hepatic Panel;	Х		Х	X 5	Х	X ⁵			х	
Acute Care Panel	Х									
PT/PTT	Х				Х				Х	
Urinalysis	Х				Х					
β-HCG in women of childbearing potential	Х				Х				X	
Optional biopsy	Х				Cycle 3 only					
Correlative Research Studies ⁶		Х			Cycle 3 only			X		
NIH Advance Directives Form	X ⁷									
Adverse Events						Continuous	assessment			
Concomitant Medications			Continuous assessment							
Phone calls q 3 months for survival status and new anti- cancer treatment										Х

¹ A complete physical exam is performed at screening. Thereafter, brief physical exams will be performed as per schedule above.

² The following imaging assessments will be performed: CT scan, MRI (if appropriate) and FDG PET. Assessments will continue until confirmatory scans for progressive disease have been obtained.

³ All ECGs will be recorded as single digital 12-lead ECG obtained after 5-10 minutes' rest in supine or semi-recumbent position. Personnel are instructed to ensure a relaxed and quiet environment with the subjects being awake and at complete rest prior and during the recordings. On day

1 of cycle 1, the ECG will be recorded within 1 hour (+15 minutes) after the end of the infusion. On day 1 of cycle 2, an ECG will be recorded at two time points: pre-dose and within 1 hour (+15 minutes) after the end of the infusion.

- ⁴ A detailed ophthalmologic examination (visual acuity, IOP, Schirmer test and slit lamp) will be done for all patients during screening within 3 weeks before the start of study treatment. After study therapy is initiated, visual acuity and slit lamp exam will be repeated before infusion in every cycle except C1D1, and at safety follow-up visit, or more frequently at investigator's and ophthalmologist/ optometrist's discretion. IOP measurement is to be repeated during anetumab ravtansine therapy if the patient receives steroid eye drops as treatment for eye toxicity; dry eye (Schirmer) test may be repeated during treatment at investigator's discretion (e.g. in case of eye dryness during anetumab ravtansine therapy). During treatment period, ophthalmologic examination can be done up to 7 days before anetumab ravtansine infusion.
- ⁵ Assessment may be performed by local laboratory if patient is unable to return to NIH.
- ⁶ At each collection: 4 mL of blood in 10 mL tiger top tube to [name] lab; three 10 mL sodium heparin (green top) tubes to NIH Flow lab.
- ⁷ As indicated in section 10.3, all subjects ≥ age 18 will be offered the opportunity to complete an NIH advanced directives form. This should be done preferably at baseline but can be done at any time during the study as long as the capacity to do so is retained. The completion of the form is strongly recommended, but is not required.

3.5 CRITERIA FOR REMOVAL FROM PROTOCOL THERAPY AND OFF STUDY CRITERIA

Prior to removal from study, effort must be made to have all subjects complete a safety visit approximately 30 days following the last dose of study therapy.

3.5.1 Criteria for removal from protocol therapy

- Requirement for therapy prohibited by protocol (see section 4.2)
- Progressive disease; however, treatment may be continued provided that the patient derives clinical benefit as determined by the investigator
- Development of secondary malignancy
- Participant becomes pregnant
- Participant requests to be withdrawn from active therapy
- Unacceptable toxicity as defined in section 3.3
- Investigator discretion

3.5.2 Off-Study Criteria

- Screening failure
- Participant requests to be withdrawn from study
- Lost to follow up
- The investigator decides to stop the study
- Death

3.5.3 Off Protocol Therapy and Off Study Procedure

Authorized staff must notify Central Registration Office (CRO) when a subject is taken off protocol therapy and when a subject is taken off-study. A Participant Status Updates Form from the web site (http://home.ccr.cancer.gov/intra/eligibility/welcome.htm) main page must be completed and sent via encrypted email to: NCI Central Registration Office [contact].

4 CONCOMITANT MEDICATIONS/MEASURES

Any medication which is considered necessary for the patient's welfare, and which is not expected to interfere with the evaluation of the study treatment or listed in section 4.2 below, may be given at the discretion of the investigator. In general, patients should be closely monitored for side effects of all concomitant medications regardless of elimination path, especially those with narrow therapeutic indices, such as warfarin, phenytoin, quinidine, carbamazepine, phenobarbital, cyclosporine, and digoxin. All concomitant medications used while patient is on study therapy (including start/stop dates, dose, frequency, route of administration and indication) must be recorded.

4.1 SUPPORTIVE CARE

4.1.1 Biologic response modifiers, such as filgrastim

Filgrastim and other hematopoietic growth factors may be used during the study in the management of acute toxicity such as febrile neutropenia when clinically indicated per ASCO Recommendations for Therapeutic Use of CSF^{17} or at the discretion of the investigator (if medically necessary, growth factors may be administered at recommended doses; however they may not be substituted for a required dose reduction

4.1.2 Blood products

Blood transfusions and chronic therapy with IV or subcutaneous erythropoietin- stimulating agents (epoetin alpha, darbepoetin alpha): These are allowed, but may not be used as a substitute for required dose reduction.

4.1.3 Other

Further supportive per NIH CC Pharmacy guidelines is permitted with the exception of interventions appearing in section 4.2.

4.2 **PROHIBITED THERAPIES**

- Platinum/pemetrexed/bevacizumab
- Other systemic anti-cancer therapy (cytotoxic therapy, targeted therapies, immunotherapy, hormonal therapy, or any other experimental or approved therapy)
- Acute steroid therapy
- Anti-arrhythmic therapy other than beta blockers of digoxin
- Any drugs with known bone marrow toxicity
- Strong inhibitors and strong inducers of CYP3A4 (listed in Appendix C). Moderate and weak CYP3A4 inhibitors should be used with caution as decrease in plasma concentrations of DM4 cannot be ruled out.
- Any drugs that inhibit renal tubular secretion (e.g. probenecid and cimetidine).

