In summary, the high tumor response rate and long-lasting responses in Study 15051 would indicate a potential for anetumab ravtansine to impart clinical benefit in an unmet medical need when given as single agent at the MTD of 6.5 mg/kg Q3W in the treatment of advanced predominantly epithelial mesothelioma and ovarian cancer. However, anetumab ravtansine may have a narrow therapeutic index, based on the severe and dose-limiting drug-related AEs observed at 7.5 mg/kg Q3W in the Study 15051, and on the fact that approximately half of the Western subjects with advanced cancer treated at the MTD of 6.5 mg/kg (BW) Q3W required dose reduction and/or treatment interruption (most commonly due to drug-related corneal toxicity, peripheral neuropathy, fatigue, asthenia/weight loss, anorexia and diarrhea). On the other hand, these events in Western subjects were non-life threatening and fully reversible (or showed a clear trend to complete resolution at the time of last follow up), and manageable by treatment modification. The Japanese subjects with advanced cancer should be carefully monitored for bone marrow toxicity and hepatotoxicity during treatment with anetumab ravtansine. The Study 15404 is ongoing and the maximum tolerated dose of anetumab ravtansine in Japanese subjects has not been determined yet. Given the clinical benefit in mesothelioma and ovarian cancer as the high unmet medical need, anetumab ravtansine is expected to have an acceptable benefit-risk ratio when given as single agent at doses up to 6.5 mg/kg Q3W in patients with advanced cancer in clinical trials.

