- **2.1.2.17** Subjects experiencing unresolved toxicity of previous antitumor therapy which is CTCAE Grade >1 before the start of study treatment, except for alopecia or hemoglobin \geq 9.0 g/dL or \geq 5.6 mmol/L.
- **2.1.2.18** Subjects with any clinical condition that is considered unstable or might jeopardize the safety of the subject and/or influence the subject's compliance in the study.
- **2.1.2.19** Subjects who have received systemic anticancer therapy within 3 weeks before the start of study treatment. Mitomycin C or nitrosoureas must be excluded within 6 weeks before the start of study treatment.
- **2.1.2.20** Subjects who have received radiotherapy to tumor lesions that would be chosen as target lesions (measurable disease) within 4 weeks before the start of treatment, except if there is objective evidence of progression of the lesion by RECIST 1.1 between the prior radiotherapy and the screening CT or MRI scan. Palliative radiotherapy to non-target lesions is allowed at the investigator's discretion.

- **2.1.2.21** Use of drugs that inhibit renal tubular secretion (e.g. probenecid and cimetidine) within 2 weeks before the start of study treatment.
- **2.1.2.22** Use of strong cytochrome P450 3A4 (CYP3A4) inhibitors or strong CYP3A4 inducers within 2 weeks before the start of study treatment.
- **2.1.2.23** Subjects who have previously received anetumab ravtansine.
- **2.1.2.24** Subjects who are concurrently receiving any other investigational agents.

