11.1.5.1 Chemical Structure

Anetumab ravtansine is an ADC consisting of a fully human IgG1 antibody (MF-T, BAY 86-1903) directed at the mesothelin antigen and conjugated to a synthetic cytotoxic anticancer agent, maytansine derivative (DM4, BAY 100-6640) as toxophore through an SPDB.

Based on the reference by Davis et al.²³, DM4 is a substrate of metabolizing enzymes CYP3A4, 3A5, and 2D6. Further the package insert of ado-trastuzumab emtansine, which also uses maytansine (referred to as DM1) conjugated to trastuzumab, indicates that the cytotoxic component is mainly metabolized by 3A4 and to a lesser extent by 3A5. Therefore, concomitant administration of strong inhibitors and inducers of CYP3A4 are prohibited in patients receiving anetumab ravtansine.

DM4-Me is a substrate of P-gp transporter and it is possible that medications that are potent inhibitors of P-gp transporter could alter the pharmacokinetic profile of DM4-Me in plasma.

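### Section 4.2 warns that moderate and weak CYP3A4 inhibitors may lower DM4, but the protocol's own pharmacology section implies they would raise it

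*Combined protocol and SAP*

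**What the plan says.** Section 4.2 (Prohibited Therapies) bans strong CYP3A4 inhibitors and strong CYP3A4 inducers on study. In the same bullet it leaves weaker inhibitors available, with a caution and a reason: "Moderate and weak CYP3A4 inhibitors should be used with caution as decrease in plasma concentrations of DM4 cannot be ruled out".

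The pharmacology behind these rules is in Section 11.1.5.1 (Chemical Structure). It states that "DM4 is a substrate of metabolizing enzymes CYP3A4, 3A5, and 2D6". For a product carrying the related maytansinoid DM1, it reports that "the cytotoxic component is mainly metabolized by 3A4 and to a lesser extent by 3A5". From this it concludes that "concomitant administration of strong inhibitors and inducers of CYP3A4 are prohibited in patients receiving anetumab ravtansine". The section does not say in which direction an inhibitor or an inducer would move DM4.

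Strong agents are handled consistently elsewhere. Exclusion criterion 2.1.2.22 rules out "Use of strong cytochrome P450 3A4 (CYP3A4) inhibitors or strong CYP3A4 inducers within 2 weeks before the start of study treatment", and Appendix C lists the strong inhibitors and inducers.

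**The concern.** The reason given in Section 4.2 runs against the metabolism described in Section 11.1.5.1. If CYP3A4 removes DM4, an inhibitor slows removal and DM4 should rise, or stay the same if the effect is negligible. Section 4.2 warns of a fall.

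An investigator deciding whether a patient can stay on a moderate or weak inhibitor, or should be switched, is told to think about lost drug effect. The expected concern is more free cytotoxin. The direction matters because Section 1.2.3.1 says that "anetumab ravtansine may have a narrow therapeutic index". Treatment starts at 6.5 mg/kg, the maximum tolerated dose in the phase I study, where 7.5 mg/kg was not tolerated and about half of Western patients at 6.5 mg/kg needed a dose reduction, an interruption or both.

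**Working it through.** The plan gives no figure to reproduce. The check compares what the sections say about direction, then confirms the sign with a simple clearance formula.

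**Coverage of CYP3A4 co-medication**

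| Group | Where covered | Rule | Direction stated for DM4 |
|---|---|---|---|
| Strong inhibitors and inducers | 2.1.2.22, 4.2, 11.1.5.1, Appendix C | Excluded at entry, prohibited on study, listed | None |
| Moderate and weak inhibitors | 4.2 only | Permitted with caution | Decrease |
| Moderate and weak inducers | Nowhere | None | None |

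**Reasoning from the text**

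1. Section 11.1.5.1 makes DM4 a substrate of CYP3A4, so CYP3A4 is a route by which DM4 is removed.
2. An inhibitor reduces removal by that route. Total clearance falls, so plasma DM4 rises.
3. An inducer increases removal by that route, so plasma DM4 falls.
4. An inhibitor could lower DM4 only if CYP3A4 were needed to form it. Neither document section describes such a mechanism. The other interaction remark in 11.1.5.1 concerns the P-gp transporter and DM4-Me, and it gives no direction either.

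**Sign check**

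Let *f* be the fraction of DM4 clearance that runs through CYP3A4, and *i* the fraction of that route that is inhibited. Remaining clearance is 1 − *f*·*i* of its uninhibited value, so

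exposure ratio = 1 / (1 − *f*·*i*).

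The documents give neither *f* nor *i*. Taking 0.2 to 0.8 for each, purely as an assumption:

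- *f* = *i* = 0.2: 1 / (1 − 0.04) = 1.04
- *f* = *i* = 0.8: 1 / (1 − 0.64) = 2.78

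The ratio exceeds 1 for every *f* and *i* strictly between 0 and 1. This confirms the sign only. It follows directly from treating CYP3A4 as a clearance route, and the range is not an estimate of the interaction: the upper end is probably too large for inhibitors described as moderate or weak.

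**The case against.** The strongest reply is that nothing the investigator must do changes. The instruction is caution in either case, strong agents are already excluded and banned, and the study calendar in Section 3.4 schedules blood counts, hepatic panels and eye examinations regardless. Section 4 also asks that patients be "closely monitored for side effects of all concomitant medications regardless of elimination path". This largely stands and is why the point is minor, although that last sentence concerns side effects of the co-medications themselves, not a rise in the study drug's payload.

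A second reply is that the toxicity link is thin. The only exposure–toxicity relation in the protocol (Section 1.2.3.1) ties corneal epitheliopathy to the AUC of the intact conjugate, not to plasma DM4. The remark about therapeutic index rests on conjugate doses. Section 11.1.5.1 names three enzymes for DM4 without giving any of them a share, and the statement that 3A4 predominates is about DM1. This stands as a limit on size: the increase could be negligible, and added toxicity is an expectation, not something the documents show. It does not make a decrease the right warning.

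A third reply is that the wrong word may be *inhibitors*, not *decrease*. The documents do not settle this. Either way the sentence is wrong as printed, and for inhibitors the correct direction is an increase.

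**Conclusion.** The concern holds. As written, the reason for caution in Section 4.2 contradicts the metabolism in Section 11.1.5.1. The conclusion rests on one assumption: that CYP3A4 acts on DM4 as a clearance route, which is the only role the protocol gives it.

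The consequence is small. It is a wording error in operative co-medication guidance with no bearing on sample size, the two-stage error rates, DLT counting or the response analysis. The number of patients likely to take a moderate or weak inhibitor is not given, so the practical reach cannot be stated. It is worth correcting because it is the only CYP3A4-specific advice for a group of drugs that patients are allowed to take.

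**What to change.** In Section 4.2, change *decrease* to *an increase* in the sentence on moderate and weak CYP3A4 inhibitors and leave the rest as it is.

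The sponsor should also confirm what was intended. If the sentence was meant for inducers, keep the corrected inhibitor sentence and add a second one advising caution with moderate and weak CYP3A4 inducers because they may lower DM4.

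The cost is a one-word edit, plus one sentence if inducers were meant. It can go into the next amendment. Design, sample size and procedures do not change.

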5 BIOSPECIMEN COLLECTION

5.1 CORRELATIVE STUDIES FOR RESEARCH

5.1.1 Induction of anti-mesothelin humoral immune response

We have previously shown that in some patients with mesothelioma and ovarian cancer there is loss of tolerance to mesothelin as reflected by development of anti-mesothelin antibodies. We propose evaluating serum samples from all patients enrolled on this study and determine if treatment with anetumab ravtansine induces a humoral immune response to mesothelin and if so correlating induction of anti-mesothelin humoral immune response with tumor characteristics (such as tumor mesothelin expression, serum mesothelin and megakaryocyte-potentiating factor (MPF) levels) as well as clinical outcome including overall survival.

5.1.1.1 Sample Collection

Samples will be collected at baseline, at the end of cycle 2 and at the end of treatment.

All blood samples will be taken by either direct venipuncture or an indwelling venous access. At each sample collection time, blood (4mL) will be drawn into a 10-mL serum separator tube (tiger top tube) labeled as follows:

- Subject ID Number
- Study Number
- Time and date of collection

5.1.1.2 Sample Processing

Please e-mail [name] at [contact] and [name] [contact] at least 24 hours before transporting samples (the Friday before is preferred).

For sample pickup, page [name].

For immediate help, call [contact] (main blood processing core number) or, if no answer, [contact] (main clinical pharmacology lab number).

For questions regarding sample processing, contact [name] by e-mail or at [contact].

Upon arrival in the CPP, each sample should be processed in the following manner:

Allow blood to clot for 10 minutes and centrifuge to separate the serum within 30 minute of collection. If necessary whole blood may be stored in the collection tubes upright and refrigerated at 4-8°C for up to 24 hours prior to centrifugation and processing. Processing within 30 minutes is strongly preferred. Transfer the serum into two (2) pre-labeled cryotubes and immediately freeze by placing on dry ice. Transfer frozen serum samples into a - 80°C freezer for storage.

Autoantibody levels will be retrospectively assessed.

5.1.1.3 Sample Storage

All serum samples will be stored frozen at approximately -80°C in the Clinical Pharmacology Program.

5.1.2 Gene expression-based characterization of the immune landscape before and after treatment with anetumab ravtansine

We will evaluate tumor biopsies before and after treatment with anetumab ravtansine using a hybridization-based digital gene expression platform nCounter (NanoString Technologies). This platform allows for unbiased multiplexed quantification of RNA transcripts achieving sensitivity comparable to quantitative reverse-transcription polymerase chain reaction (Q-RT-PCR), without any enzymatic reaction involved in the process. We have expertise in the use of this technology for the characterization of purified cell subsets and also for the study of the changes that occur in human tumors, as a consequence of a given treatment, using tumor core biopsy tissues. This analysis can be performed on flash frozen biopsies without any further isolation or enrichment of specific cell types. We will also use immunohistochemistry and immunofluorescence techniques to characterize diverse immune cell subpopulations and alterations with tumor biopsies of patients before and after treatment.

For the present study, we will screen pre- and post-treatment samples for the expression of markers of immune cell subsets (CD3, CD8, CD4, etc.), local production of cytokines (interferon-gamma, tumor necrosis factor-alpha, etc.) and chemokines (CXCL13, CCL5, etc.), adhesion molecules and others. The purpose of this study is to characterize the molecular changes that occur within the tumors following treatment with anetumab ravtansine. The ultimate goal is to gain a better understanding of the mechanism of action of this treatment, and to identify molecular correlates of clinical outcomes such as objective responses and/or improved survival.

In order to achieve these goals, flash frozen samples will be subjected to total RNA isolation followed by hybridization with capture and detection probes specific for 620 transcripts, including genes involved in the regulation of the immune function and also markers expressed by tumor cells and tumor stroma. To cover those target transcripts, a combination of a commercially available pre-designed probe set (GX Human Immunology v2, NanoString Technologies) will be used in combination with a custom-designed code set of thirty additional targets (Panel Plus, NanoString Technologies). Hybridization complexes will be quantified using a NanoString nCounter Analysis System, at the Genomics Core Facility of the Center for Cancer Research, NCI.

Results obtained by this approach will be correlated with data obtained from immunohistochemistry and pathology analysis of tumor biopsies as well as with data from analysis of peripheral blood populations, for a comprehensive study of the mechanism of action of anetumab ravtansine in lung cancer and mesothelioma patients.

